12.2 Analysis Sets

Parts A

Assignment of subjects to analysis sets will be done before the clinical data lock for the study. The analysis set will be defined separately for Part A

Safety Set

The Safety Set will include all subjects who received at least 1 dose of study drug. The Safety Set will be used for all safety analyses.

Full Analysis Set (FAS)

The FAS will include all subjects who carry the intended CFTR allele mutation and received at least 1 dose of study drug. The FAS will be used to summarize subject demographics and baseline characteristics, and for analyses of all efficacy endpoints, unless otherwise specified.

All Subjects Set

The All Subjects Set will include all subjects who received at least 1 dose of study drug. This analysis set will be used for all individual subject data listings and disposition summary tables, unless otherwise specified.

12.3 Statistical Analysis

12.3.1 General Considerations

Parts A

Data from Part A will be analyzed separately.

Continuous variables will be summarized using the following descriptive summary statistics: number of subjects (n), mean, SD, SE, median, minimum value (min), and maximum value (max). The precision of the measurement for each continuous variable will be specified in the SAP.

Categorical variables will be summarized using counts and percentages. Percentages will be presented to 1 decimal place.

Treatment-emergent (TE) period for Parts A and B will include the time from the first dose of study drug in the respective Part through 28 days after the last dose, or the completion of study participation date, whichever is earlier.

Baseline for Part A, unless otherwise specified, is defined as the most recent nonmissing measurement (scheduled or unscheduled) collected prior to the first dose of study drug in Part A. For ECGs, baseline will be the average of the 3 pretreatment measurements on Day 1.

Absolute change from baseline will be calculated as postbaseline value – baseline value.

Relative change from baseline will be calculated as (postbaseline value – baseline value)/baseline value.

12.3.2.4 Study Drug Exposure and Compliance

[figure not shown]
Parts A

[figure not shown]
Study drug compliance will be measured by the exposure ratio, which is calculated as: $100 \times [1 - (Total number of days study drug interruption) / (Duration of study drug exposure in days)]. The total number of days of study drug interrupted is defined as the sum of (number of days of study drug interrupted in each interruption interval); where number of days of study drug interrupted in each interval is defined as the interruption end date - the corresponding interruption start date + <math>1$.

Study drug exposure will be summarized based on the Safety Set in terms of the duration of treatment a subject received (in days), defined as the last day – the first day of study drug plus 1, regardless of study drug interruption.

In addition, percentage of tablets taken will also be summarized based on the FAS, and will be calculated as $100 \times [(\text{total number of tablets dispensed}) - (\text{total number of tablets returned})] / (total number of tablets planned to be taken per day × duration of study drug exposure in days).$

Duration of treatment and exposure ratio will be summarized using descriptive statistics.

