2 PROTOCOL SYNOPSIS

Title A Phase 3 Study Evaluating the Pharmacokinetics, Safety, and Tolerability of VX-659/TEZ/IVA Triple Combination Therapy in Cystic Fibrosis Subjects 6 Through 11 Years of Age

Brief Title Evaluation of VX-659/TEZ/IVA in Cystic Fibrosis Subjects 6 Through 11 Years

Clinical Phase and Clinical Study Type

Phase 3, pharmacokinetic (PK), safety, and tolerability

Objectives

Part A

Primary Objective

To evaluate the PK of VX-659, tezacaftor (TEZ), and ivacaftor (IVA) when dosed in triple combination (TC)

Secondary Objectives

- To evaluate the PK of TEZ and IVA metabolites
- To evaluate the safety and tolerability of VX-659/TEZ/IVA

Endpoints Part A

Primary Endpoint

PK parameters of VX-659, TEZ, and IVA, including C_{max}, C_{trough}, and AUC_{0-T}

Secondary Endpoints

- PK parameters of TEZ and IVA metabolites, including C_{max}, C_{trough}, and AUC_{0-τ}
- Safety and tolerability as determined by adverse events (AEs), clinical laboratory values, standard 12-lead ECGs, vital signs, and pulse oximetry

Number of Part A Subjects

Approximately 12 subjects are planned for enrollment.

Study **Population**

Male and female cystic fibrosis (CF) subjects 6 through 11 years of age who are homozygous for F508del (F/F genotype) or heterozygous for F508del and a minimal function mutation that is not responsive to TEZ, IVA, or TEZ/IVA (F/MF genotypes).

Investigational

Part A Drug

Active substance: VX-659/TEZ/IVA

Activity: CFTR correctors (VX-659 and TEZ) and CFTR potentiator (IVA) (increased chloride ion secretion)

Strength and route of administration: 120-mg VX-659/50-mg TEZ/75-mg IVA fixed-dose combination (FDC) tablet for oral administration AND 75-mg IVA tablet for oral administration

Dose administered:

VX-659 120 mg qd/TEZ 50 mg qd/IVA 75 mg q12h; $1 \times VX$ -659/TEZ/IVA FDC tablet in the morning and $1 \times IVA$ tablet in the evening

Study Duration

Part A

Excluding the Screening Period, subjects will participate in the study for up to 6 weeks (± 7 days)

Study Design

This is a Phase 3, 2-part (Parts A), multicenter study evaluating the PK, safety, and tolerability of VX-659/TEZ/IVA TC therapy in CF (F/F and F/MF genotypes) subjects 6 through 11 years of age (inclusive).

[figure not shown]
Part A

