A schematic of the study design for Part A is provided below. Approximately 12 subjects (F/F or F/MF genotypes) are planned for enrollment. During the Treatment Period, subjects will be administered VX-659/TEZ/IVA for approximately 15 days. A review of safety, tolerability, and available PK data will be completed by an internal Vertex team after Part A

Additional subjects may be enrolled as needed in Part A,

based on emerging PK data,

[figure not shown]
Part A Study Design

IVA: ivacaftor; n: number of subjects; TEZ: tezacaftor

VX-659/TEZ/IVA will be administered from Day 1 through Day 15. On Day 15, only the morning dose will be administered.

Parts A Doses			
Subjects Weight	VX-659 Dose	TEZ Dose	IVA Dose
Part A			
All weights	$120 \mathrm{mg} \mathrm{qd}$	50 mg qd	75 mg q12h

IVA: ivacaftor; qd: daily; q12h: every 12 hours; TEZ: tezacaftor

[figure not shown]
Assessments Parts A

PK Assessments:

- PK parameters for VX-659, TEZ, and IVA
- PK parameters for TEZ and IVA metabolites

Safety Assessments:

AEs, clinical laboratory assessments (serum chemistry, hematology, coagulation studies, and urinalysis), standard 12-lead ECGs, vital signs, pulse oximetry, ophthalmologic examinations, and physical examinations (PEs)

Statistical Analyses

Data from Parts A will be analyzed separately.

Part A

Approximately 12 subjects will be enrolled in Part A. Sample size calculations were determined based on VX-659 PK using noncompartmental analysis-based parameters, such as clearance and volume of distribution. Based on the variability observed in adults, data from 12 subjects will allow 80% power to target a 95% CI within 60% and 140% of the geometric mean estimate of clearance for VX-659.

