9.6 Administration

9.6.1 Dosing

Part A

On Day 1 through Day 15, VX-659/TEZ/IVA will be orally administered with water. On Day 15, only the morning dose of VX-659/TEZ/IVA will be administered.

Study drug should be administered within approximately 30 minutes of the start of a fat-containing snack or meal, such as a standard "CF" meal or snack according to the following guidelines:

- 1. Morning dose of study drug will be administered at the site on Days 1, 2, 8, and 15.
- 2. Study drug will be administered after all predose assessments have been performed.
- 3. All doses of study drug (morning and evening, as applicable) should be administered at approximately every 12 hours (± 1 hour) on each dosing occasion (e.g., if the morning doses of study drug are administered at 08:00 hour on Day 1, all subsequent morning doses should be administered between 07:00 hour and 09:00 hour).
- 4. Study drug tablets will be administered within 5 minutes of each other.
- 5. Study drug will be administered with approximately 240 mL (approximately 1 cup, 8 ounces, or half a pint) of water.
- 6. At the Day 1 Visit, all subjects will be observed for 4 hours after the morning dose of the study drug.
- 7. The date, amount taken, and time of study drug administration including whether food was taken with each dose, will be recorded for 2 days before PK sample collection and on the days of PK sample collection.

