9.6.2.2 Evening Dose of Study Drug

Parts A

If a subject misses the evening dose of IVA and recalls within 6 hours, the subject should take his/her dose with food. If more than 6 hours have elapsed after his/her usual dosing time, the subject should skip that dose and resume his/her normal schedule for the following dose.

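### The percentage-of-tablets formula counts a Day 15 evening tablet that is not scheduled, so a 15-day completer who doses exactly to plan scores 96.7% instead of 100%

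*Protocol*

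**What the plan says.** **Schedule.** Under the dose administered in the protocol Synopsis, each subject takes one fixed-dose combination (FDC) tablet in the morning and one ivacaftor (IVA) tablet in the evening. Section 9.6.2.2 confirms that the evening dose is IVA alone ("If a subject misses the evening dose of IVA and recalls within 6 hours"). The last day differs. The notes to the Part A design in the Synopsis and in Section 9.1 state: "On Day 15, only the morning dose will be administered". Section 9.6.1 repeats it: "On Day 15, only the morning dose of VX-659/TEZ/IVA will be administered".

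**Formula.** Section 12.3.2.4 gives two adherence figures.

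- The named compliance measure is based on days of interruption: "Study drug compliance will be measured by the exposure ratio".
- A tablet count is added: "In addition, percentage of tablets taken will also be summarized based on the FAS". Its numerator is tablets dispensed minus tablets returned. Its denominator is "total number of tablets planned to be taken per day × duration of study drug exposure in days".

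Duration of exposure is "defined as the last day – the first day of study drug plus 1, regardless of study drug interruption".

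Nothing in Section 12.3.2.4 or elsewhere in the protocol adjusts the denominator for the morning-only last day.

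**The concern.** The denominator multiplies one daily tablet count by a number of calendar days, so every day on drug counts as a two-tablet day. Day 15 is planned as a one-tablet day. The denominator is then one tablet larger than the schedule for every subject who takes the final dose as planned.

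The exposure ratio counts whole days of interruption. The tablet percentage is the only summary in the section that works at tablet level, so it is where a single skipped evening IVA tablet would be expected to show. As written, perfect adherence looks like about one missed tablet in 30. A subject who leaves out the Day 15 dose altogether can score higher than one who takes it.

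**Working it through.** The protocol states no numerical adherence figure, so there is none to reproduce. The check applies its formula to its own schedule.

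**Inputs**

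- Tablets on a full dosing day: 1 FDC + 1 IVA = 2 (Synopsis).
- Tablets on Day 15: 1, the morning FDC tablet (Synopsis, Sections 9.1 and 9.6.1).
- Duration D = last day − first day + 1 (Section 12.3.2.4). For Day 1 to Day 15, D = 15 − 1 + 1 = 15.
- Assumption: every untaken tablet is returned, so that dispensed minus returned equals tablets taken.

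**Tablets scheduled against tablets in the denominator**

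- Scheduled, with a morning-only final day: 2 × (D − 1) + 1 = 2D − 1. At D = 15 this is 29 (15 FDC + 14 IVA).
- Denominator as written: 2D. At D = 15 this is 30.

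**Scores for a subject who takes the Day 15 morning dose (D = 15)**

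| Earlier tablets missed | As written | Against the schedule | Difference (percentage points) |
|---|---|---|---|
| 0 | 29/30 = 96.7% | 29/29 = 100% | 3.3 |
| 1 | 28/30 = 93.3% | 28/29 = 96.6% | 3.2 |
| 2 | 27/30 = 90.0% | 27/29 = 93.1% | 3.1 |

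**Comparison with a subject who stops a day early.** All tablets taken through the Day 14 evening and none afterwards gives D = 14 and 28/(2 × 14) = 28/28 = 100%. This subject left out a scheduled tablet and still scores above the perfect completer.

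**Visit window.** Table 3-2 allows ±1 day for the Day 15 visit. The protocol does not say that the morning-only dose moves with the visit. If it does, dosing to plan scores 27/28 = 96.4% at D = 14 and 31/32 = 96.9% at D = 16. The conclusion does not rest on these two figures.

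**The case against.** The arithmetic is not in dispute. The case against raising the point is about weight, place and completeness.

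- **Nothing depends on the figure.** The exposure ratio is the named compliance measure. The tablet percentage has no threshold and defines no analysis set, and Part A has a single treatment, so no comparison between arms can be biased. This stands, and it caps the point at minor.
- **The SAP could settle it.** Section 12 describes itself as a summary and leaves detail to the SAP, which is not at hand. This has some force. But the protocol does not leave the formula open: it writes one out, and that formula disagrees with its own schedule. Copied faithfully into the SAP, the error goes with it.
- **The daily count could be read as varying by day.** That would need a sum over days. The text multiplies a single daily count by a duration.
- **A perfect completer could still reach 100%.** An unreturned tablet counts as taken, so a lost tablet would give 30/30. That is true, and it is why the claim assumes complete return. A lost tablet hiding the shortfall does not make the denominator right.
- **The correction leaves other half-day cases.** A subject who takes the Day 8 morning tablet, is then stopped under a protocol rule and never resumes has taken 7 × 2 + 1 = 15 tablets, and scores 15/16 = 93.8% before and after the change. A subject who takes everything through Day 14 and omits Day 15 still scores 28/28, because the denominator follows actual duration. Both observations are correct. They lie outside this point, and the change makes neither worse.

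**Conclusion.** The concern holds. For a 15-day completer the stated denominator is 30 tablets where the schedule has 29. Perfect adherence is reported as 96.7%, and completers with one or two missed tablets are understated by 3.2 and 3.1 percentage points. The error is systematic and always downward.

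The finding is restricted in two ways. It covers only subjects who take the planned morning-only final dose; for those who stop earlier, the denominator is not in error on this ground. It also assumes that all untaken tablets are returned.

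The consequence is confined to one descriptive summary. The exposure ratio, the analysis sets, and the PK and safety endpoints are not touched.

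**What to change.** In Section 12.3.2.4, for subjects who take the planned morning-only final dose at the Day 15 visit, set the denominator to (tablets planned per day × duration) − 1. That is 2D − 1, or 29 when D = 15. For subjects who stop earlier, keep 2D. Keep the duration definition as it is, including its disregard of interruptions.

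A 15-day completer who doses to plan then scores 29/29 = 100%. If the final dose does move with the visit window, the same rule gives 27/27 and 31/31. Real omissions stay visible: a child whose last tablet is the Day 14 morning one, and who omits the scheduled Day 14 evening tablet, still scores 27/28 = 96.4%.

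The cost is one line in the protocol, carried into the SAP. There is no operational cost, and no dosing rule or data collection changes.

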9.6.2 Missed Doses

9.6.2.1 Morning Dose of Study Drug

Parts A

If a subject misses the morning dose of study drug and recalls within 6 hours, the subject should take his/her dose with food. If more than 6 hours but fewer than 12 hours have elapsed after his/her usual dosing time, the subject should take the morning dose of study drug but skip the evening dose of study drug. If more than 12 hours have elapsed after his/her usual dosing time, the subject should skip the morning dose of study drug and take the evening dose of study drug.

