10 STUDY DRUG INFORMATION AND MANAGEMENT

Parts A

Study drug refers to VX-659/TEZ/IVA.

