10.3 Study Drug Supply, Storage, and Handling

Parts A

Table 10-1 provides the study drug information. The investigator, or an authorized designee (e.g., a licensed pharmacist), will ensure that all investigational product is stored in a secured area, under recommended storage conditions, and in accordance with applicable regulatory requirements. Detailed instructions regarding the storage, handling, and dispensation of the study drug will be provided in the Pharmacy Manual.

Table 10-1 Study Drug: Strength/Dosing Form/Route

Drug Name, Dosing Form, Route	Strength		
	Part A: All Subjects		
VX-659/TEZ/IVA, FDC tablet, oral			
VX-659	120 mg		
TEZ	50 mg		
IVA	75 mg		
IVA, tablet, oral	75 mg		

FDC: fixed-dose combination; IVA: ivacaftor; TEZ: tezacaftor

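### The percentage of tablets taken pools the morning FDC tablet with the evening IVA tablet, so it cannot show adherence to VX-659 and TEZ

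*Protocol*

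**What the plan says.** Section 12.3.2.4 of the protocol names the exposure ratio, which is built from days of interruption, as the compliance measure. It then adds a second summary: "percentage of tablets taken will also be summarized based on the FAS". The numerator is all tablets dispensed minus all tablets returned. The denominator is "total number of tablets planned to be taken per day × duration of study drug exposure in days". Duration of exposure is "the last day – the first day of study drug plus 1, regardless of study drug interruption". Nothing in the section separates tablet types, and section 10 uses one term for the whole regimen: "Study drug refers to VX-659/TEZ/IVA".

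The regimen consists of two products. The synopsis gives one "FDC tablet in the morning and" one IVA "tablet in the evening". Table 10-1 in section 10.3 lists "VX-659/TEZ/IVA, FDC tablet, oral" (VX-659 120 mg, TEZ 50 mg, IVA 75 mg) apart from the 75-mg IVA tablet. Section 9.6.1 limits Day 15 to the morning dose.

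The missed-dose rules allow either tablet to be lost alone. When a morning dose is more than 12 hours late, section 9.6.2.1 says that "the subject should skip the morning dose of study drug and take the evening dose of study drug". When it is 6 to 12 hours late, the morning dose is taken and the evening one is skipped. Under section 9.6.2.2, an evening dose more than 6 hours late is also skipped.

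**The concern.** Only the FDC tablet contains VX-659 and TEZ. A count that treats the two tablets as interchangeable cannot say which was missed, and the protocol's own missed-dose rules produce days on which just one of them is. The other compliance measure does not fill the gap: the exposure ratio counts days in interruption intervals and does not distinguish products.

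The PK of VX-659, TEZ and IVA is the primary endpoint, with about 12 subjects planned. Anyone interpreting one subject's exposure would want to know how much of the FDC was taken. As defined, the tablet percentage does not answer that. It also reads below 100% for a subject who took every scheduled tablet.

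**Working it through.** The protocol states no compliance figure, so there is none to reproduce. The check applies the formula in section 12.3.2.4 to the planned course.

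**Inputs**
- Planned tablets per day: 1 FDC + 1 IVA = 2 (synopsis, Table 10-1).
- Duration of exposure for a completed course: 15 days (sections 9.6.1 and 12.3.2.4).
- Tablets actually scheduled: 15 FDC + 14 IVA = 29, because Day 15 has no evening dose.
- Dispensed minus returned is taken to equal tablets swallowed.

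**Full adherence**
- Formula denominator: 2 × 15 = 30.
- Result: 29/30 = 96.7%. With the ±1-day window on the Day 15 visit and a morning-only last day, it is 27/28 = 96.4% for 14 days and 31/32 = 96.9% for 16 days.

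**Effect of one missed tablet**
- FDC-only measure: 1/15 = 6.7 points.
- Pooled formula: 1/30 = 3.3 points, whichever tablet was missed.

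**Only FDC tablets missed (k of them), every evening IVA tablet taken**
- FDC-specific = 100 × (15 − k)/15
- Pooled = 100 × (29 − k)/30

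| k | FDC-specific | Pooled | FDC shortfall | Pooled shortfall | Ratio of shortfalls |
|---|---|---|---|---|---|
| 1 | 93.3% | 93.3% | 6.7 | 6.7 | 1.00 |
| 3 | 80.0% | 86.7% | 20.0 | 13.3 | 0.67 |
| 5 | 66.7% | 80.0% | 33.3 | 20.0 | 0.60 |

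The ratio starts at 1.00 because the pooled figure has already lost 3.3 points to the evening tablet on Day 15 that is not scheduled.

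**Both tablets missed on the same 3 days**
- Pooled: (29 − 6)/30 = 76.7%.
- FDC-specific: 12/15 = 80.0%. Here the pooled figure is the lower one (shortfall ratio 23.3/20.0 = 1.17).

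**What a pooled 80.0% can mean**
- 24 of the 29 scheduled tablets were taken, so 5 were missed.
- All 5 FDC: FDC intake 10/15 = 66.7%.
- All 5 IVA: FDC intake 15/15 = 100%.
- Mixed patterns fall between.

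**FDC doses documented elsewhere (nominal schedule)**
- Morning doses given at the site: Days 1, 2, 8 and 15 (section 9.6.1), supervised under section 10.6.
- Doses recorded individually: PK days 1, 8 and 15 (Table 3-2) and the 2 days before each (section 9.6.1), which adds Days 6, 7, 13 and 14.
- Together: Days 1, 2, 6, 7, 8, 13, 14 and 15, which is 8 of 15. The other 7 (Days 3–5 and 9–12) rest on tablet counts and review at visits.

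**The case against.** The strongest objection is that nothing turns on this number. The exposure ratio is the named compliance measure and the tablet percentage is an addition to it. No adherence threshold, analysis set or PK exclusion in the protocol uses it, and the PK analysis is left to the clinical pharmacology analysis plan. Predose samples on Days 8 and 15 measure VX-659 directly. All of this stands, and it keeps the point minor.

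A second objection is that a split by product is ordinary SAP detail. That would hold if the protocol had left the calculation open. It writes the formula out in full, and the formula as written gives the pooled figure. The SAP, which is not shown, may still split it, and the accountability records in section 10.4 would allow that.

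Three stronger readings are tempting, and the documents do not support them.
- A reader might infer that pooling halves every shortfall in VX-659 and TEZ dosing. One-half is only the cost of each additional FDC tablet missed alone. On the protocol's denominator the total shortfall ratio is 1.00 at one missed tablet and 0.67 at three, and it exceeds 1 when both tablets are missed on the same days.
- A reader might take tablet counts as the main evidence of VX-659 intake. More than half of the FDC doses are supervised or individually recorded.
- A reader might conclude that a misleading count hides a failure to reach steady state by Day 15. The protocol gives no VX-659 half-life from which to judge that, and doses on Days 13 to 15 are among those recorded.

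**Conclusion.** The point holds as a minor flaw in a formula that the protocol itself fixes. The pooled percentage cannot show adherence to VX-659 and TEZ. It can overstate FDC intake (80.0% against 66.7% when five FDC tablets are missed alone) or understate it (80.0% against 100% when five IVA tablets are missed alone). It also reads 96.7% for a subject who took everything scheduled over 15 days.

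This rests on three assumptions: the planned number per day is read as 2 for every exposure day, which is the natural reading of section 12.3.2.4; the course lasts 15 days with a morning-only last day; and unreturned tablets were taken. The primary analysis and the analysis sets are unaffected.

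**What to change.** In section 12.3.2.4, or in the SAP if it is still open, define the percentage of tablets taken separately for the FDC tablet and the evening IVA tablet. For each product, use tablets dispensed minus tablets returned over the tablets actually scheduled for that product during the subject's exposure: 15 FDC and 14 IVA for a 15-day course. A fully adherent subject then reads 100% on both. A pooled figure may be kept as a supplement, preferably over the 29 scheduled tablets.

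The cost is one sentence and one extra table row. The two products are already listed separately in Table 10-1, and section 10.4 already requires dispensed and returned amounts to be kept. No dose, missed-dose rule or data collection changes.
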